5.1.1 Efficacy Variables Primary Endpoint

Overall Survival (OS): Time from randomization to death. Subjects alive or lost to follow-up are censored at the date the subject was last known to be alive.

5.1.2 Efficacy Variables Secondary Endpoints

Centrally imaging results will determine the subject's best tumor response and time of progression according to RECIST 1.1. for the following endpoints. In addition, supportive tumor response and progression will be analyzed based on investigator assessment.

- Progression Free Survival (PFS): Time from randomization to either documented radiological progression (PD) or death. Subjects alive and free of progression are censored at the last tumor assessment date when alive and free of progression were known. And if there is no baseline tumor assessment data for subjects, the subjects are censored at the date of randomization.
- Objective Response Rate (ORR): Proportion of subjects with a Best Overall Response of Complete Response (CR) or Partial Response (PR).
- Disease Control Rate (DCR): Proportion of subjects with a Best Overall Response of complete response (CR) or partial response (PR), or stable disease (SD).

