### 8.2.2. Secondary Efficacy Endpoints

- Progression Free Survival (PFS): Time from randomization to either radiological progression or death. Subjects alive and free of progression at the end of study (EOS) are censored.
- Objective Response Rate (ORR): Percentage of subjects with a Best Overall Response of Complete Response (CR) or Partial Response (PR).
- Disease Control Rate (DCR): Proportion of subjects with a Best Overall Response of complete or partial response, or stable disease.
- Global health status/quality of life score according to European Organization for Research and Treatment of Cancer Quality of Life Questionnaire-Core 30 (EORTC QLQ-C30) and EORTC QLQ-STO22
- Each dimension response according to EuroQol 5-Dimension 5-Level (EQ-5D-5L) Questionnaire

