Table 4. Time Point Response (subjects with non-target lesions only)

Non-Target Lesions	New Lesions	Overall Response
CR	No	CR
Non-CR/non-PD	No	Non-CR/non-PD
Not evaluated	No	Inevaluable (NE)
Unequivocal PD	Yes or No	PD
Any response	Yes	PD

The best overall response without confirmation of complete or partial response is defined as the best response across all time points. When there are more than one response, it will be selected as the best overall response according to the order of CR > PR > SD > NON-CR / NON-PD > PD > NE. The minimum duration for SD to decide best response is 6 weeks.

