7.5.4 Other Secondary Efficacy Analysis

All other secondary efficacy endpoints will be analyzed in the ITT, FAS, and PPS using two-sided test at the alpha=0.05 level of significance, with no adjustments for multiplicity.

- Disease Control Rate (DCR): Proportion of subjects with a Best Overall Response (determined by the central imaging analysis facility) of complete or partial response (CR or PR), or stable disease (SD).
- Global health status/quality of life score according to European Organisation for Research and Treatment of Cancer Quality of Life Questionnaire-Core 30 (EORTC QLQ-C30) and EORTC QLQ-STO22.
- Each dimension response according to EuroQol 5-Dimension 5-Level (EQ-5D-5L) Questionnaire.

For the DCR, the same statistical method that is used in ORR will be performed.

Each derived score from the European Organisation for Research and Treatment of Cancer Quality of Life Questionnaire-Core 30 (EORTC QLQ-C30) and EORTC QLQ-STO22 will be summarized by descriptive statistics by treatment group for each cycle. Each derived score from EORTC QLQ-C30 and EORTC QLQ-STO22 will also be analyzed using analysis of covariance (ANCOVA) models for each cycle with the derived change from baseline score as dependent variable, treatment group and the randomization stratification variables as factors, and the baseline score of the corresponding questionnaire as a covariate. Least

squares mean difference and 95% confidence interval with corresponding p-value for comparing two treatment groups will be presented.

For EuroQol 5-Dimension 5-Level (EQ-5D-5L), the number and percentage (%) of subjects for each level of each dimension will be presented for each cycle for both treatment groups. EQ VAS data will be analyzed using analysis of covariance (ANCOVA) models for each cycle with the derived change from baseline score as dependent variable, treatment group as a factor and the randomization stratification variables, the baseline score of the corresponding questionnaire as covariates. Least squares mean difference and 95% Confidence interval with corresponding p-value for comparing two treatment groups will be presented.

Data will be summarized in the following tables.

- Table. Disease Control Rate [Independent Central Review] – ITT
- Table. Disease Control Rate [Independent Central Review] – FAS
- Table. Disease Control Rate - [Investigator Review] – ITT
- Table. Disease Control Rate - [Investigator Review] – FAS

- Table. EORTC QLQ-C30 [Parameter] – ITT

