10.2 Summary Statistics

Summary statistics for continuous variables/endpoints will be presented with number of observations (n), mean, standard deviation (SD), median, minimum (min), and maximum (max). Summary statistics for categorical variables/endpoints will be presented with counts (n) and percents. Unless otherwise specified, denominator of percentage is number of subjects included in the analysis set by each group.

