13. CHANGE FROM PROTOCOL

Protocol v5.0 Location(s)	SAP Location(s)	Protocol v5.0 Language	SAP Language Changed from Protocol v5.0	Reason of Change
Section 8.1.1 p.73	Section 3.7.1 p.15	"Where HR (hazard ratio) is the ratio of median overall survival of Placebo and Rivoceranib* group."	"where HR (hazard ratio) is the ratio of median overall survival of denotes the hazard ratio for Rivoceranib group relative to Placebo group. "	Clarify language in the protocol.
Section 8.1.3 p.74	Section 3.7.3 p.16	"325 events (413 subjects) are needed."	" a total of 325 events (413 subjects) are needed to provide approximately 80% power for Overall Survival. "	Clarify language in the protocol.
Section 8.3.2 p.75	Section 4.1 Section 4.2 Section 4.3 Section 4.4 p.17	"ITT set consists of data from all subjects who are randomized." "The analysis for primary endpoint, OS and the secondary endpoints of PFS and ORR will be conducted in the ITT set." "Safety set consists of data from all subjects who received at least one dose of Rivoceranib or placebo." "The FAS will be used for all efficacy analyses." "The PPS will be used for all efficacy analyses."	"ITT set consists of data from all subjects who are randomized into the study. " " The analysis The ITT set will be used for the primary efficacy analyses endpoint, OS and the secondary endpoints of PFS and ORR will be conducted in the ITT set. " "Safety set consists of data from all subjects in the ITT population who received at least one dose of Rivoceranib or placebo." "The FAS will be used for all supportive efficacy analyses." "The PPS will be used for all supportive efficacy analyses."	Clarification that ITT set will be used for the primary efficacy analyses, and FAS and PPS will be used for supportive efficacy analyses.

Protocol v5.0 Location(s)	SAP Location(s)	Protocol v5.0 Language	SAP Language Changed from Protocol v5.0	Reason of Change
Appendix 2: Table 3 p.91	Section 5.1 Table 4 Table 5 p.18	Table title: Time Point Response	Table title: Time Point Response (subjects with target and non-target lesion) Added table 5: Time Point Response (subjects with non-target lesion only)	Clarified on the original table and added a table to define response for subjects with non-target lesion only.

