Section 8.2.1 p.74 Section 8.3.4 p.76	Section 5.1.1 p.19 Section 7.5.2 p.29	“Overall Survival (OS): Time from randomization to death. Subjects alive or lost to follow-up at the end of study (EOS) are censored.”	“Overall Survival (OS): Time from randomization to death. Subjects alive or lost to follow-up at the end of study (EOS) analysis cut-off point are censored at the date the subject was last known to be alive. ”	Clarified overall survival censoring.
Section 8.2.2 p.74 Section 8.3.5 p.76	Section 5.1.2 p.19 Section 7.5.3 p.30	“Subjects alive and free of progression at the end of study (EOS) are censored.”	“Subjects alive and free of progression at the end of study (EOS) are censored at the last tumor assessment date when alive and free of progression were known. ”	Clarified progression free survival censoring.
Section 8.3.5 p.76	Section 5.1.2 p.19	“Progression Free Survival (PFS): Time from randomization to either radiological progression (determined by the central imaging analysis facility) or death from any cause.”	Centrally imaging results will determine the subject's best tumor response and time of progression according to RECIST 1.1. for PFS, ORR and DCR. In addition, supportive tumor response and progression will be analyzed based on investigator assessment.	Added supportive tumor response and progression analyses based on investigator assessment.
Section 8.3.4 p.76	Section 7.5.2 p.29	“The comparison of OS between the two treatment groups will be performed with a stratified log-rank	“The comparison of OS between the two treatment groups will be performed with a log-rank test stratified on the randomization stratification variables	Due to the occurrence of several very small strata for non-measurable subjects, it is not meaningful to conduct

Protocol v5.0 Location(s)	SAP Location(s)	Protocol v5.0 Language	SAP Language Changed from Protocol v5.0	Reason of Change
		test at the two-sided alpha=0.05 level of significance.”	[Geographic region (Asia vs. North America/Europe) , Prior ramucirumab treatment (Yes vs. No) , and Treatment therapy line (3rd vs. ≥ 4th)] at the two-sided alpha=0.05 level of significance.”	stratified analyses using all four randomization stratification variables. The measurable vs. non-measurable stratification criteria will not be utilized in all stratified analyses.

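### DCR counts only CR, PR and SD, so non-progressing disease in subjects without target lesions (Non-CR/non-PD) is scored as no disease control

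*SAP*

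**What the plan says.** Protocol 3.2.1 admits subjects with measurable or only nonmeasurable evaluable disease, and measurability is a randomization factor (Protocol 4.2, SAP 3.4).

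Protocol 8.2.2 defines DCR as "Proportion of subjects with a Best Overall Response of complete or partial response, or stable disease". Protocol Appendix 2 has a time-point table for target plus non-target disease only, so Non-CR/non-PD is not an overall response there.

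SAP 5.1 adds Table 4 for subjects with non-target lesions only. The change log in SAP 13 records it, under a different table number: "Added table 5: Time Point Response (subjects with non-target lesion only"). Best overall response is then chosen by the "order of CR > PR > SD > NON-CR / NON-PD > PD > NE". The next sentence gives a minimum duration for SD alone: "The minimum duration for SD to decide best response is 6 weeks".

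The DCR definition was not changed to match. SAP 5.1.2 gives "Proportion of subjects with a Best Overall Response of complete response (CR) or partial response (PR), or stable disease (SD"), and SAP 7.5.4 repeats it for the central read as a best overall response "of complete or partial response (CR or PR), or stable disease (SD"). Under SAP 10.2, unless otherwise specified, the "denominator of percentage is number of subjects included in the analysis set by each group". Nothing else is specified for DCR. SAP 9 plans a DCR table for the Non-measurable subgroup.

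**The concern.** The SAP created a response category for a group of eligible subjects but kept an endpoint definition written before that category existed. A subject whose non-target disease persists without progressing stays in the DCR denominator but cannot enter the numerator. At the same scan that subject is progression-free for PFS.

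Three things are at stake:

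- Overall DCR is understated in both arms.
- The Non-measurable DCR table is largely emptied of meaning. Subjects read centrally as non-target-only can count only through CR, so for them it repeats the ORR table. An apparent lack of disease control there could come from the definition alone.
- The coding is left open. A literal programmer scores failure, while one who treats the category as equivalent to SD scores success, with no stated minimum duration.

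DCR is an other secondary endpoint, tested at two-sided 0.05 without multiplicity adjustment and outside the OS, PFS, ORR sequence. No confirmatory claim depends on it.

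**Working it through.** **1. Responses set against the definition.** For a subject with non-target lesions only:

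| State at the scan | SAP Table 4 | Rank in best response | In DCR as written | PFS progression |
|---|---|---|---|---|
| All lesions gone | CR | 1 | yes | no |
| Persisting, not progressing | Non-CR/non-PD | 4 | no | no |
| Unequivocal progression or new lesion | PD | 5 | no | yes |
| Not evaluated | NE | 6 | no | no |

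PR (rank 2) and SD (rank 3) cannot arise. In this group DCR = CR rate = ORR. SAP 13 has no row on DCR, so the change log does not close the gap.

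**2. Formula.** Let s be the non-target-only share and q the proportion of those subjects whose best response is Non-CR/non-PD. In each arm

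DCR with the category − DCR as written = s × q.

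With s equal in both arms, the between-arm difference falls by s × (q_test − q_placebo).

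**3. Inputs.**

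- From the documents: about 459 subjects, 2:1, hence 306 vs 153.
- Not in the documents: s and the DCR rates. The plan gives no DCR figure to reproduce.
- Assumed: s from 2% to 20%; disease control of 40% vs 15% or 40% vs 25%, the same in both disease types; CR near zero in non-target-only subjects. Then DCR as written = DCR × (1 − s).

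**4. Is the range of s sensible?** Four two-level factors give 16 strata, 8 of them non-measurable. Shares of 2, 5, 10 and 20% of 459 are 9, 23, 46 and 92 subjects, on average 1.1, 2.9, 5.7 and 11.5 per non-measurable stratum. SAP 13 reports "several very small strata for non-measurable subjects". That fits a low share better than a high one but does not bound it, so 20% is shown as an extreme.

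**5. Results for 40% vs 15%.** Affected subjects are 306 × s × 0.40 and 153 × s × 0.15.

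| s | DCR as written | Difference (points) | Affected, test drug | Affected, placebo |
|---|---|---|---|---|
| 0 | 40.0% vs 15.0% | 25.0 | 0 | 0 |
| 2% | 39.2% vs 14.7% | 24.5 | 2.4 | 0.5 |
| 5% | 38.0% vs 14.25% | 23.75 | 6.1 | 1.1 |
| 10% | 36.0% vs 13.5% | 22.5 | 12.2 | 2.3 |
| 20% | 32.0% vs 12.0% | 20.0 | 24.5 | 4.6 |

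**6. If disease control differs by disease type.** The fall in the difference at s = 2, 5, 10 and 20% is:

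- 20% vs 7.5% in non-target-only subjects: s × 12.5 = 0.25, 0.6, 1.25 and 2.5 points.
- 60% vs 30%: s × 30 = 0.6, 1.5, 3.0 and 6.0 points.
- 30% in both arms: 0.

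**7. Effect on the test.** This uses exact enumeration of an unstratified pooled z test at two-sided 0.05, as an approximation to the planned stratified Cochran-Mantel-Haenszel test.

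- 40% vs 15%: power is 99.99% at s = 0 and still 99.89% at s = 20%.
- 40% vs 25%: power is 90.0, 89.1, 87.6, 85.0 and 78.5% at s = 0, 2, 5, 10 and 20%.

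**The case against.** The strongest reply is that this is a small matter described with assumed numbers. Every input to the size except the sample size and allocation is an assumption. At a share of 2% to 5% the difference moves by 0.5 to 1.25 points (40% vs 15%). The visible loss of power, to 78.5%, needs both the extreme share and the smaller assumed effect. SAP 9 declares subgroup p-values non-inferential, makes subgroup analysis depend on sufficient numbers, and limits the study report to informative analyses. All of this stands, and it is why the point ranks as worth fixing rather than critical.

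It can also be said that the SAP never states in words that Non-CR/non-PD is a DCR failure, and that the mock-up tables and imaging guideline are not available here. That is true. But the definition, the separate ranking and the full-set denominator leave no other literal reading, and no visible text maps the category to SD.

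The contrast with PFS needs care: the subject is progression-free at that scan, not for good, and SD shorter than 6 weeks also fails DCR without being a PFS event. That does not rescue the rule, since a non-target-only subject fails however long the disease stays stable.

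Finally, one could keep the protocol definition as the main analysis and add the broader one as a sensitivity analysis. The arms would still be comparable, but the main DCR would then be unable to register stable disease in a group the trial chose to enrol. Either way the SAP must state its rule.

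**Conclusion.** The concern holds. By the SAP's own tables, a subject with non-target-only disease and a best overall response of Non-CR/non-PD counts as not controlled, and for such subjects DCR duplicates ORR. This is a stated rule that misclassifies a category the SAP itself introduced. It follows from the text without any assumption.

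The size does rest on assumptions. Under equal disease control across disease types, DCR and the absolute difference shrink by the factor (1 − s). At s = 5% and 40% vs 15%, that is 25.0 to 23.75 points, with about 6 of 306 and 1 of 153 subjects affected. The direction is usually towards a smaller difference, so the rule does not favour the test drug. OS, PFS, ORR and the fixed testing sequence are untouched. The clearest harm is to the Non-measurable DCR table.

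**What to change.** Before unblinding:

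- In SAP 5.1.2 and 7.5.4, define DCR as a best overall response of CR, PR, SD or Non-CR/non-PD.
- In SAP 5.1, state that the 6-week minimum for SD also applies to Non-CR/non-PD. Scans are due about every 8 weeks and may be taken up to 7 days early, so an on-schedule scan at about 7 weeks (8 − 1) still qualifies. The rule matters mainly for early unscheduled scans.
- Use the same definition for the central read, the investigator read and all DCR subgroup tables.
- Add a row to SAP 13 recording the change from Protocol 8.2.2 and 8.3.6.
- Keep the CR/PR/SD version as a sensitivity analysis.

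The cost is a phrase in two sections, one sentence, one change-log row and one line of code, with no new data. The downside is a departure from the protocol's DCR wording, which the sensitivity analysis covers.

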5.2 Pharmacodynamic Variables

Levels of vascular endothelial growth factor (VEGF), soluble VEGF receptor-1 (sVEGFR-1), sVEGFR-2, and sVEGFR-3 will be evaluated at baseline (on Cycle 1 Day 1 prior to first dose), on Day 1 (± 3 days) of each subsequent treatment cycle, and at the End of Treatment/Discontinuation visit.

All subjects will be evaluated at baseline for single nucleotide polymorphisms (SNPs) in VEGFR-2 (rs1870377, rs2305948, and rs17709898) that may provide genotype information that correlates to response to VEGFR-2 inhibition therapy.

5.3 Patient Reported Outcome

European Organisation for Research and Treatment of Cancer Quality of Life Questionnaire-Core 30 (EORTC QLQ-C30) and the European Organisation for Research and Treatment of Cancer Quality of Life Questionnaire-the gastric cancer specific module (EORTC QLQ-STO22) were used to evaluate patient reported outcome.

EORTC QLQ-C30 is a 30-item core-cancer-specific questionnaire-integrating system for assessing the health-related QOL of cancer subjects participating in international clinical trials. The questionnaire incorporates 5 functional scales (physical, role, cognitive, emotional and social), 4 symptom scales (fatigue, pain, nausea/vomiting, appetite), a global QOL scale and single items for the assessment of additional systems commonly reported by cancer subjects (e.g., constipation, diarrhoea, sleep disturbance and financial). All items are scored on 4-point Likert scales, ranging from 1 ('not at all') to 4 ('very much'), with the exception of two items in the global QOL scale which use modified 7-point linear analog scales.

Table 5. Scoring the QLQ-C30 version 3.0

	Scale	Number of items	Item range*	Version 3.0 Item numbers	Function scales
Global health status / QoL					
Global health status/QoL	QL2	2	6	29, 30	
Functional scales					
Physical functioning	PF2	5	3	1 to 5	F
Role functioning	RF2	2	3	6, 7	F
Emotional functioning	EF	4	3	21 to 24	F
Cognitive functioning	CF	2	3	20, 25	F
Social functioning	SF	2	3	26, 27	F
Symptom scales / items					
Fatigue	FA	3	3	10, 12, 18	
Nausea and vomiting	NV	2	3	14, 15	
Pain	PA	2	3	9, 19	
Dyspnoea	DY	1	3	8	
Insomnia	SL	1	3	11	
Appetite loss	AP	1	3	13	
Constipation	CO	1	3	16	
Diarrhoea	DI	1	3	17	
Financial difficulties	FI	1	3	28	

* Item range is the difference between the possible maximum and the minimum response to individual items; most items take values from 1 to 4, giving range=3.

For all scales, the RawScore (i.e., RS) is the mean of the component items:

$$\text{RawScore} = \text{RS} = (I_1 + I_2 + \dots + I_n) / n$$

Using the RawScore, Functional scales:

$$\text{Scale} = [1 - (\text{RS} - 1) / \text{range}] * 100$$

Symptom scales / items and Global health status / QoL:

$$\text{Score} = [(\text{RS} - 1) / \text{range}] * 100$$

EORTC QLQ-STO22 is a 22-item gastric cancer-specific questionnaire-integrating system for assessing the health-related QOL of gastric cancer subjects.

Table 6. Scoring the QLQ-STO22

	Scale name	Number of items	Item range	QLQ-STO22 Item numbers
Functional scales				
Body image	STOBI	1	3	19
Symptom scales				
Dyspnoea	STODYS	3	3	1-3
Pain	STOPAIN	4	3	4-7
Reflux symptoms	STORFX	3	3	8-10
Eating restrictions	STOEAT	4	3	11-13,16
Anxiety	STOANX	3	3	17,18,20
Dry mouth	STODM	1	3	14
Taste	STOTA	1	3	15
Body image	STOBI	1	3	19
Hair loss	STOHL	2/1	3	21, 22*

* Item 22 is an optional item and depends on the answer to item 21. Item 22 should only be answered and assessed if 'yes' has been answered to item 21.

For all scales, the RawScore (i.e., RS) is the mean of the component items:

$$\text{RawScore} = \text{RS} = (I_1 + I_2 + \dots + I_n) / n$$

Using the RawScore, Functional scales and Symptom scales:

$$\text{Score} = [(\text{RS} - 1) / \text{range}] * 100$$

Only when at least half of the items for each sub-scale have been answered, RawScore of the scale will be calculated. The RawScore is defined as the average of the items that are answered from the respondent excluding the unanswered items. When less than half of the items are answered, the corresponding score is considered as missing.

5.3.1 EuroQol 5-Dimension 5-Level (EQ-5D-5L) Questionnaire

It consists of EQ-5D-5L descriptive system and the visual analogue scale (VAS). The descriptive system comprises the 5 dimensions (mobility, self-care, usual activities, pain/discomfort, anxiety/depression) and

each dimension has 5 levels.

5.4 Patient Reported Outcome Secondary Endpoints

The following secondary endpoints will be analyzed based on patient reported outcomes.

- Global health status/quality of life score according to European Organisation for Research and Treatment of Cancer Quality of Life Questionnaire-Core 30 (EORTC QLQ-C30) and EORTC QLQ-STO22
- Each dimension response according to EuroQol 5-Dimension 5-Level (EQ-5D-5L) Questionnaire

5.5 Gastric Cancer History and Current Cancer Status

5.5.1 Gastric Cancer History

All gastric cancer history within 3 year prior to screening will be collected. History of gastric cancer shall include date of diagnosis, method for diagnosis, stage at initial diagnosis, location of primary tumor at diagnosis (Gastric [\geq 5 cm below GEJ] vs. GEJ), location of metastases (metastases to other organs such as lung, liver metastasis) etc.

